### 7.2.1. Adverse Event Reporting Period

Adverse events and serious adverse events will be collected under this extension study protocol from the administration of the first dose of extension study drug until the Follow-up visit approximately 30 days after the last dose of study drug or the date of initiation of another investigational agent or hormonal therapy affecting the hypothalamic-pituitary-gonadal axis or surgical intervention for endometriosis, whichever occurs first, as also specified in the study Schedule of Activities (Section 1.1). Serious adverse events reported to the investigator after the safety reporting period should be reported to the sponsor if the investigator assesses the event as related to the study drug treatment.

Reporting instructions for serious adverse events are provided in Section 7.6.

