### 7.1. Adverse Event Definitions

#### 7.1.1. Adverse Event

**Adverse event:** An adverse event is any unfavorable and unintended sign (including an abnormal laboratory finding), symptom, or disease (new or exacerbated) temporally associated with the use of a medicinal product, whether or not related to the medicinal product.

Events meeting the definition of an adverse event **include:**

- A worsening, excluding minor fluctuations, in the nature, severity, frequency, or duration of a pre-existing condition;
- Development of an intercurrent illness during the study;
- Development of symptoms that may or may not be related to the use of a concomitant medication or investigational product;
- Injury or accidents: If a medical condition is known to have caused the injury or accident, the medical condition and the accident should be reported as 2 separate medical events (eg, for a fall secondary to dizziness, both “dizziness” and “fall” should be recorded separately); and
- An investigational abnormality (eg, laboratory parameter, vital sign, ECG) only if the abnormality is considered clinically significant by the investigator based on at least one of the following criteria:
  - Induces clinical signs or symptoms;
  - Requires active intervention;
  - Requires interruption or discontinuation of study drug.

---

Events that **do not** meet the definition of an adverse event include:

- Medical or surgical procedures (eg, surgery, endoscopy, tooth extraction, transfusion); the condition that leads to the procedure is an adverse event;
- Pre-existing diseases or conditions present or detected before the start of study drug administration that do not worsen;
- Situations where an untoward medical event has not occurred (eg, planned hospitalization for an elective procedure, with elective defined as known or planned at the time of signing of the informed consent);
- Endometriosis-associated pain is not considered an adverse event in this study because it is being quantitatively measured as the primary efficacy endpoint.

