## 9.5. Safety Analyses

Safety assessments will include treatment-emergent adverse events, vital signs and weight, physical examinations, clinical laboratory tests, 12-lead ECG, and bone mineral density with DXA. Safety summaries by treatment group will be performed using treatment groups defined based on the actual randomized treatment received in the parent study.

The treatment-emergent period will be defined as the period of time from the first dose date and time of randomized study drug in the parent study through 30 days after the last dose of study drug, or the date of initiation of another investigational agent or hormonal therapy affecting the hypothalamic-pituitary-gonadal axis or surgical intervention for endometriosis, whichever occurs first. Safety will be assessed through summaries of adverse events, the frequency of treatment discontinuations due to adverse events, laboratory evaluations, and bone densitometry results.

The severity of all adverse events is to be evaluated by the investigator based on the National Cancer Institute CTCAE. All adverse events will be coded to preferred term, high level term, and system organ class using MedDRA 20.0 or higher. The incidence of adverse events will be presented by MedDRA system organ class and preferred term, relationship to study drug treatment, and severity. A patient reporting the same adverse event more than once is counted once, and at the maximum severity or strongest relationship to study drug treatment when calculating incidence.

Laboratory data consist of chemistry, hematology, and hormonal tests. Only data collected by the central laboratory will be used to do the analyses. The National Cancer Institute CTCAE will be used to categorize toxicity grade for the laboratory parameters. Shift tables will be provided for each gradable parameter to summarize baseline toxicity grade versus post-baseline toxicity grade. For laboratory parameters that are not gradable by the CTCAE, a shift table based upon the normal range (low, normal, and high) will be provided for each parameter to summarize the parent study Baseline versus post-baseline results. All data will be listed and summarized by

visit. The change from parent study Baseline to each post-baseline study visit will be presented by parent study treatment group for each laboratory test.

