### 5.10.3. Prohibited Non-Drug Therapies

Surgical treatment of endometriosis is prohibited from the Week 24/Baseline visit until the patient's final study visit unless urgently needed for patient safety.

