An endometrial biopsy will have been performed at the parent study Week 24 visit for all patients who participated in MVT-601-3101 (see MVT-601-3101 protocol for details). An endometrial biopsy is required at Week 52 and the Early Termination visit for all patients. This procedure is not required at the Early Termination visit in patients whose last dose of study drug was taken during Week 32 or earlier or within four weeks after completion of the Week 52 endometrial biopsy. However, the procedure may be done if it will aid in the evaluation of an ongoing adverse event. An endometrial biopsy at Week 104 is recommended for all patients who complete the open-label extension ; however, patients will have the option to opt out. Safety monitoring for this study includes physical examination, clinical laboratory tests, pregnancy tests, and adverse event collection at each visit. Clinical chemistries will be collected at each visit. A complete blood count will be collected at Week 24/Baseline, Week 28, Week 36, Week 52, Week 65, Week 78, Week 91, and Week 104. At the Week 24/Baseline visit, Week 52 visit, and Week 104 visit, additional tests include fasting (at least 8 hours, other than water) glucose, lipid profile, and hemoglobin A1c.

Electrocardiograms will be performed at the Week 24/Baseline and the Week 52 visits.

A mammogram will be performed at Week 52 or at Week 104/Early Termination for women who are or become  $\geq 40$  years old during the study (see Section 6.5.2.9).

Bone densitometry will occur at the Week 24/Baseline, Week 36, Week 52, and Week 104/Early Termination visits. Follow-up of bone densitometry findings will proceed according to the rules described in Section 6.5.2.6.

Bone densitometry and ECGs will be submitted for central reading.

Study drug compliance will be reviewed at each visit. Fasting (other than water) for at least 8 hours is required prior to blood sampling on Week 24/Baseline and Week 52/Early Termination visits and for 1 hour after administration of the study drug in the clinic. Laboratory requisitions must indicate whether or not the patient was not fasted for their chemistry and lipid testing.

Refer to the Schedule of Activities (see Section 1.1) for information about study procedures during the Open-Label Treatment Period.

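### Sections 7.2.1 and 9.5 close the adverse-event windows at endometriosis surgery, HPG-axis hormonal therapy or another investigational agent even while study drug continues, so later on-drug events go uncounted

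*Protocol*

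**What the plan says.** Section 7.2.1 collects adverse events and serious adverse events from the first extension dose. Collection ends at the Follow-up visit, about 30 days after dosing ends, unless one of three other dates comes earlier: "or the date of initiation of another investigational agent or hormonal therapy affecting the hypothalamic-pituitary-gonadal axis or surgical intervention for endometriosis, whichever occurs first". The section states that the Schedule of Activities carries the same rule. Once the period has closed, a serious event goes to the sponsor only if the investigator considers it related to study drug.

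Section 9.5 starts the treatment-emergent period at the first randomized dose of the parent trial and runs it "through 30 days after the last dose of study drug, or the date of initiation of another investigational agent or hormonal therapy", with endometriosis surgery again among the end points and the earliest date governing.

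Other sections bear on whether these end points can fall during dosing:

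- Section 5.10.3 bars surgical treatment of endometriosis "until the patient's final study visit unless urgently needed for patient safety".
- Section 5.10.1 prohibits hormonal drug classes through the Follow-up visit. It does not say what happens to study drug if one is taken.
- Section 4.5 lists the events that lead to removal from therapy. Endometriosis surgery and prohibited hormone use are not among them.
- Section 6.2 includes in routine safety monitoring "pregnancy tests, and adverse event collection at each visit". The Schedule of Activities has an adverse-event entry at every visit, and its footnote gives a start point but no early stop.

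Incidence of adverse events is a named safety endpoint at Week 52 and Week 104 (Section 3).

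**The concern.** A treatment-emergent window should cover all time on drug and a defined period after it. Closing the period early when another therapy or an operation intervenes makes sense after the last dose, because later events are then hard to attribute. Applied during dosing, the same rule removes time in which the woman is still exposed to the product under study.

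The women removed are not a random subset. They are those who needed urgent surgery or received added hormones, and the cut falls on the day of the operation or the first dose of the other agent. What follows, including the post-operative course on an estrogen-containing regimen, would not appear in the treatment-emergent tables of a study whose purpose includes long-term safety.

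The conflict over collection is a second problem. A site that follows Section 7.2.1 stops recording, while a site that follows the Schedule continues, so data after a trigger could differ between sites.

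**Working it through.** The plan gives no figure to reproduce. The check is textual, with a short calculation for scale.

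**Can a trigger occur on drug?**

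| Question | Source | Answer |
|---|---|---|
| Must study drug have stopped for the trigger to end collection? | 7.2.1 | No such condition |
| Must it have stopped for the trigger to end the treatment-emergent period? | 9.5 | No such condition |
| Can endometriosis surgery happen during treatment? | 5.10.3 | Yes, if urgently needed |
| Does surgery or prohibited hormone use require removal from therapy? | 4.5 | Not listed; only the opinion-based undue-risk and gross-noncompliance criteria could apply |
| Does collection continue after a trigger? | 6.2, Schedule | Yes, at each visit |

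It follows that a woman can reach the end of both windows while still taking study drug. If a site follows the Schedule and records a later event, Section 9.5 still leaves it out of the treatment-emergent summaries.

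**One woman, for illustration.** Suppose a trigger at Week 40 and dosing to Week 104.

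- On-drug weeks outside the window: 104 − 40 = 64.
- Share of her 80 extension weeks: 64/80 = 80%.
- Share of the 104 weeks from the first parent-study dose, where the Section 9.5 window starts: 64/104 ≈ 62%.

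**The whole study.** Inputs from the protocol are about 800 women and 80 weeks of open-label treatment. The share f with an on-treatment trigger is not given and is assumed. Triggers are taken as spread evenly over the 80 weeks, and every woman is taken to stay on drug to the end.

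- Total on-drug extension time: 800 × 80 = 64,000 person-weeks.
- Average loss per affected woman: 80/2 = 40 weeks.
- Time lost: 800 × f × 40; share lost: f/2.

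| Assumed f | Women | Person-weeks lost | Share of 64,000 |
|---|---|---|---|
| 1% | 8 | 320 | 0.5% |
| 2% | 16 | 640 | 1.0% |
| 5% | 40 | 1,600 | 2.5% |

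**Direction.** Section 9.5 counts each woman once per event. Shortening her window can remove her from the numerator but cannot add her to it, and she stays in the Safety Population denominator. The percentage with a given event can therefore only fall or stay the same.

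**The case against.** The strongest reply is that the clause was meant only to shorten the 30-day tail after treatment. Section 6.3 uses nearly the same list to time the post-treatment Follow-up visit, and Section 7.2.1 attaches the clause to that visit. This is probably the intent. It is not what Section 9.5 says, though, and a programmer working from that section would end the period at the trigger date whether or not dosing continued.

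A second reply is that collection is required elsewhere: at each visit, at each telephone contact, and under the general instruction in Section 7.2 to document all adverse events. Section 7.6 requires every serious event within 24 hours regardless of relationship. This largely stands. A reader might infer that serious-event reporting is seriously weakened; with Section 7.6 and the Schedule in place, the documents do not support that. These provisions do not repair the counting rule in Section 9.5.

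Third, the situation should be rare. Hormones are prohibited, surgery is exceptional, and Section 4.5 leaves room to remove a woman for undue risk or gross noncompliance. An event already counted before the trigger remains counted, and the safety analysis is descriptive. All of this limits the size of the problem but does not make the rule correct.

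Two wider readings should be set aside. A reader might take the trigger to be any hormonal therapy, but the text limits it to therapy acting on the hypothalamic-pituitary-gonadal axis. A reader might also add Section 7.1.1, which says "Endometriosis-associated pain is not considered an adverse event in this study because it is being quantitatively measured as the primary efficacy endpoint", and conclude that the reason for surgery disappears as well. The same section treats the condition leading to a procedure as an adverse event, and the exclusion of pain is a choice with a stated reason. It is not part of this point.

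**Conclusion.** The rule is wrong as written in Sections 7.2.1 and 9.5 of the Amendment 2 text and should be corrected. On-drug events after a trigger fall outside the treatment-emergent summaries, and Section 7.2.1 contradicts Section 6.2 and the Schedule on collection.

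The effect on total exposure is probably small: about 0.5% to 2.5% of on-drug extension time if 1% to 5% of women are affected. Those rates are assumptions, as are the even spread of triggers and full continuation on drug. The documents do not support a claim of large bias in overall incidence. They do support a selective loss, concentrated in women with surgery or added hormones, that can only lower the reported percentages.

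One limit remains. The later protocol version breaks off before its Sections 7 and 9, so its wording of these windows cannot be checked. The parts that are shown (Sections 4.5, 5.10.3 and 6.3) add no rule that would close the gap.

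**What to change.** - In Sections 7.2.1 and 9.5, state that another investigational agent, HPG-axis hormonal therapy or endometriosis surgery ends the period only when it occurs after the last dose of study drug. While dosing continues, all adverse events are collected and counted.
- Align both sections with the Schedule of Activities, including the statement in Section 7.2.1 that the Schedule contains its rule.
- Flag in the listings any event that follows an on-treatment trigger, so that possible confounding is visible.

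The cost is about one sentence in each section and a listing flag; visits and data collection stay as they are. The downside is that a few events confounded by surgery or added hormones enter the tables, which the flag addresses. If the later version already contains such a condition, no change is needed there. Whether dosing should continue after such an event is a clinical matter for the sponsor, and the change takes no position on it.

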### 7.3. Assigning Causal Relationship to Study Drug

The reasonable possibility of the relationship of an adverse event to study drug(s) is to be assessed with careful medical consideration at the time of evaluation of an adverse event. The following definitions are to be used for the relationship of the adverse event to study drug:

- **Probably related:** A clinical event, including laboratory test abnormality, with a reasonable time sequence to administration of the drug, unlikely attributed to concurrent disease or other drugs or chemicals, and that follows a clinically reasonable response on re-administration (rechallenge) or withdrawal (dechallenge).
- **Possibly related:** A clinical event, including laboratory test abnormality, with a reasonable time sequence to administration of the drug but that could also be explained by concurrent disease or other drugs or chemicals. Information on drug withdrawal may be lacking or unclear.
- **Not related:** A clinical event, including laboratory test abnormality, with a temporal relationship to drug administration that makes a causal relationship improbable and/or in which other drugs, chemicals, or underlying disease provide a plausible explanation.

All adverse events, whether or not related to study drug, must be fully and completely documented on the adverse event page of the eCRF and in the patient's clinical record. In the event a patient is withdrawn from the study because of an adverse event, it must be recorded on the eCRF as such.

### 7.4. Assigning Severity Rating for Adverse Events

Severity describes the intensity of a specific event (as in mild, moderate, or severe myocardial infarction); the event itself, however, may be of relatively minor medical significance, such as a severe headache. This is not the same as "serious," which is based on patient/event outcome or action taken.

The investigator must determine the severity of each adverse event according to the National Cancer Institute CTCAE. For terms not specified with the CTCAE, the criteria in [Table 7-1](#) should be used to determine the grade severity.

**Table 7-1 Criteria for Determining the Grade/Severity of Adverse Event Terms Not Specified by the National Cancer Institute CTCAE**

Grade	Criteria
1/Mild	Asymptomatic or mild symptoms, clinical or diagnostic observations only; intervention not indicated
2/Moderate	Minimal, local, or noninvasive intervention indicated; limiting age-appropriate instrumental activities of daily living
3/Severe or medically significant	Not immediately life-threatening; hospitalization or prolongation of hospitalization indicated; disabling; limiting self-care activities of daily living
4/Life-threatening	Life-threatening consequences; urgent intervention indicated
5/Death	Death related to adverse event

CTCAE = Common Terminology Criteria for Adverse Events.

Adverse event severity should be recorded in the appropriate section of the adverse event case report form and in the patient's source documents.

## 7.5. Adverse Events of Clinical Interest Reporting

Adverse events of clinical interest in this study are defined as any increase in ALT or AST  $\geq 3$  x ULN.

Any ALT or AST elevation of this degree or greater occurring during the Open-Label Treatment Period or the Follow-Up visit should be reported to the sponsor using the Serious Adverse Event Form **within 24 hours of the study site personnel's knowledge of the event** (see Section 7.6), **even if the event does not meet serious adverse event criteria**. Additional instructions for evaluating patients with an increase in ALT or AST  $\geq 3$  x ULN may be found in [Appendix 7](#).

### 7.5.1. Criteria for Temporary Withholding of Study Drug in Association with Liver Test Abnormalities

Hepatic enzymes will be monitored in accordance with FDA drug-induced liver injury guidelines [[FDA, 2009](#)].

If the following liver test abnormalities develop, study drug should be withheld immediately with appropriate clinical follow-up (including repeat laboratory tests, until a patient's laboratory profile has returned to normal/baseline status), and the event reported as a serious adverse event:

- ALT or AST  $> 8$  x ULN; or
- ALT or AST  $> 5$  x ULN and persists for more than 2 weeks; or
- ALT or AST  $> 3$  x ULN **and** total bilirubin  $> 2$  x ULN **or** the INR  $> 1.5$ ; or
- ALT or AST  $> 3$  x ULN with appearance of fatigue, nausea, vomiting, right upper quadrant pain or tenderness, fever, rash and/or eosinophilia ( $> 5\%$ ).

Rechallenge may be considered if an alternative cause for the abnormal liver tests (ALT, AST, total bilirubin) is discovered and the laboratory abnormalities resolve to normal or baseline values. The investigator and sponsor must discuss and agree with any decision to rechallenge.

Rechallenge should not occur when the etiology of the liver test abnormalities is considered possibly drug induced.

#### **7.5.2. Criteria for Permanent Discontinuation of Study Drug in Association with Liver Test Abnormalities**

Study drug treatment should be discontinued permanently if all of the following 4 criteria are met (ie, potential severe drug-induced liver injury/Hy's law case):

1. AST or ALT increases to  $\geq 3$  x ULN; AND
2. Total bilirubin increases to  $> 2$  x ULN or INR  $> 1.5$ ; AND
3. Alkaline phosphatase value does not reach 2 x ULN; AND
4. No alternative cause explains the combination of the above laboratory abnormalities; important alternative causes include, but are not limited to the following:
  - Hepatobiliary tract disease;
  - Viral hepatitis (eg, hepatitis A/B/C/D/E, Epstein-Barr virus);
  - Exposure to hepatotoxic agents/drugs or hepatotoxins, including herbal and dietary supplements, plants, and mushrooms;
  - Alcoholic hepatitis;
  - Nonalcoholic steatohepatitis;
  - Autoimmune hepatitis.

If an alternative cause for hepatotoxicity is identified, then it should be determined (based on the severity of the hepatotoxicity or event) whether study drug treatment should be withheld or permanently discontinued as appropriate for the safety of the patient.

#### **7.6. Serious Adverse Event Reporting**

Using a Safety Reporting Form, all serious adverse events must be reported **within 24 hours of the study site personnel's knowledge of the event**, regardless of the investigator assessment of the relationship of the event to study drug.

The contact information for submission of serious adverse events, adverse events of clinical interest (defined in Section 7.5), and events of overdose is available on the Serious Adverse Event report form and is as follows:

**For questions on Serious Adverse Event/Adverse Event of Clinical Interest reporting, please call:**

- North/South America: PPD
- Europe, Asia-Pacific, and Africa: see region-specific phone numbers accompanying the Safety Reporting Form

The initial report should include:

- Study number (MVT-601-3103);
- Site address and number;
- Investigator name;
- Patient ID number, sex, and age;
- Details of study drug administration;
- The date of the report;
- A description of the serious adverse event (event term, seriousness of the event, date of onset, intensity);
- Causal relationship to the study drug.

If the patient died, the report should include the cause of death as the event term (with death as outcome) and whether or not the event leading to death was related to study drug treatment, as well as the autopsy findings if available.

Do not delay reporting a suspected serious adverse event in order to obtain additional information. Any additional information, if collected, can be reported as a follow-up to the initial report. All serious adverse events will be followed until resolution, until the event has stabilized, and/or reached a new baseline. All serious adverse events continuing at the completion of the study must be assessed or followed to determine outcome.

